4.2.3. Elimination from ATP cohort for immunogenicity

4.2.3.1. Excluded subjects

All eliminations from the study 201330 [DTPA (BOOSTRIX)-048 PRI] will be applicable for this follow up study except for the visit specific elimination codes (2090, 2100 and 2120).

A subject will be excluded from the ATP cohort immunogenicity under the following conditions

A subject will be excluded from the ATP cohort for immunogenicity when he/she is excluded from the ATP cohort for safety (see Section [4.1.3](#)).

CONFIDENTIAL201334 [DTPA (BOOSTRIX) -049 BST: 048]
Statistical Analysis Plan Final

The following additional codes will be used:

Code	Condition under which the code is used	Visit (timepoints) where the code is applicable	Applicable for analysis set (Safety, immunogenicity)
2010	
Protocol violation (inclusion/exclusion criteria not fulfilled)
 
 Window from DOB to vaccination is 11-18(+30 days) months of age according to the routine national/ local immunization schedule or as specified in the SPM Healthy subjects as established by medical history and clinical examination before entering into the study. Previous booster vaccination against Hib, diphtheria, tetanus, pertussis, pneumococcus, hepatitis B and/or poliovirus since the conclusion visit of study 201330 [DTPA (BOOSTRIX)-048 PRI]. Subjects born to mothers who were vaccinated in 116945 [DTPA (BOOSTRIX)-047] study and having completed their primary vaccination series as per protocol requirement in study 201330 [DTPA (BOOSTRIX)-048 PRI]. 
Also inherited from the 048 study.
	Visit 1/2	Immunogenicity
2040	
Administration of any medication forbidden by the protocol
 
 Administration of immunoglobulins and/or any blood products during the period within three months before the booster dose of study vaccines or planned administration during the study period. 
Also inherited from the 048 study.
	Visit 2/3	Immunogenicity
2050	
Underlying medical condition forbidden by the protocol =>
 
Subjects may be eliminated from the ATP cohort for immunogenicity if, during the study, they incur a condition that has the capability of altering their immune response (e.g. any confirmed or suspected immunosuppressive or immunodeficient condition) or are confirmed to have an alteration of their initial immune status.
 
Also inherited from the 048 study.
	Visit 2/3	Immunogenicity
2080	
Subjects did not comply with vaccination schedule
 
Inherited from the 048 study.
	Carried forward from previous study	Immunogenicity
2090	
Subjects did not comply with blood sample schedule(date of blood sampling not corresponding to adapted protocol intervals or unknown blood sample date) => 21-48 days from vaccination (Visit 2)
	Visit 3	Immunogenicity
2100	
Serological results not available for antigens POST vaccination (including lost samples, blood sample not done, unable to test, absence of parallelism) => no immunogenicity results available at visit 3.
	Visit 3	Immunogenicity

2120	Obvious incoherence, abnormal serology evolution or error in data (incoherence between CRF and results, wrong sample labelling)	Visit 3	Immunogenicity
------	---	---------	----------------

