### 1.2.2. Rationale for the study design

This phase IV study is a follow-up of the study 201330 [DTPA (BOOSTRIX)-048 PRI] where infants in both the groups received *Infanrix hexa* co-administered with *Prevenar*

13 as part of the primary vaccination *series*. The immunogenicity and safety of *Infanrix hexa* when given as a booster dose ***according to the routine national/ local immunization schedule or as specified in the SPM*** will be evaluated. Subjects will receive *Prevenar 13* ***according to the routine national/ local immunization schedule or as specified in the SPM*** as a co-administered vaccine in this study. (Amended 12 December 2016)

This study will have two groups:

- dTpa Group: This group will consist of infants born to mothers belonging to the dTpa Group in study 116945 [DTPA (BOOSTRIX)-047], i.e., mothers who received a single dose of *Boostrix* during pregnancy and a dose of placebo immediately post-delivery and infants who ***received full*** primary vaccination course ***as per protocol requirement*** in the study 201330 [DTPA (BOOSTRIX)-048 PRI]. All infants in this group will receive a booster dose of *Infanrix hexa* co-administered with *Prevenar 13* ***according to the routine national/ local immunization schedule or as specified in the SPM***. (Amended 12 December 2016).
- Control Group: This group will consist of infants born to mothers belonging to the Control group in study 116945 [DTPA (BOOSTRIX)-047], i.e., mothers who received a single dose of placebo during pregnancy and a dose of *Boostrix* immediately post-delivery and infants who ***received full*** primary vaccination course ***as per protocol requirement*** in the study 201330 [DTPA (BOOSTRIX)-048 PRI]. All infants in this group will receive a booster dose of *Infanrix hexa* co-administered with *Prevenar 13* ***according to the routine national/ local immunization schedule or as specified in the SPM***. (Amended 12 December 2016).

The study will be open-label since the treatment allocation is similar between the two groups. Also, the data related to the study groups will be unblinded at the end of study 116945 [DTPA (BOOSTRIX)-047].

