3.3. Primary endpoint

- Immunogenicity with respect to components of *Infanrix hexa*.
 - Anti-diphtheria, anti-tetanus, anti-HBs, anti-poliovirus type 1, anti-poliovirus type 2, anti-poliovirus type 3 and anti-polyribosyl-ribitol phosphate (anti-PRP) seroprotection status, one month after the booster dose.
 - Booster response to PT, FHA and PRN antigens, one month after the booster dose.

Refer to section 5.3.2 for the definition of the booster response

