4.1.4. According-to-protocol cohort for analysis of immunogenicity

The ATP cohort for analysis of immunogenicity will include all evaluable subjects from the ATP cohort for analysis of safety:

- Who meet all eligibility criteria.
- Who received all doses of vaccine in the primary study 201330 [DTPA (BOOSTRIX)-048 PRI].
- Who comply with the procedures and intervals defined in the protocol (refer to Table 5 of the protocol).
- Who do not meet any of the criteria for elimination from an ATP analysis (refer to Section 6.7.2 of the protocol).
- Who did not receive a product leading to elimination from an ATP analysis as listed in Section 6.7.2 of the protocol,
- Who did not present with a medical condition leading to elimination from an ATP analysis as listed in Section 6.8 of the protocol,
- For whom data concerning immunogenicity endpoint measures are available. This will include subjects for whom assay results are available for antibodies against at least one study vaccine antigen component after vaccination.
- The interval between the vaccination visit and post-booster blood sampling, considered for inclusion of a subject will be 21–48 days.

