5.3. Immunogenicity

5.3.1. Analysis of immunogenicity planned in the protocol

The primary analysis will be based on the ATP cohort for analysis of immunogenicity. If in any vaccine group, the percentage of enrolled subjects excluded from this ATP cohort is more than 5%, a second analysis based on the TVC will be performed to complement the ATP analysis. All analyses will be descriptive.

For each group, at each time point that a blood sample result is available:

- Seropositivity rates against PT, FHA and PRN antigens and pneumococcal antigens (1, 3, 4, 5, 6A, 6B, 7F, 9V, 14, 18C, 19A, 19F, 23F) with exact 95% CI [Clopper, 1934] will be calculated.
- Seroprotection rates against diphtheria toxoid, tetanus toxoid, HBs, PRP antigen and poliovirus types 1, 2, 3 antigens (with exact 95% CI [Clopper, 1934]) will be calculated.
- Percentage of subjects with anti-pneumococcal serotypes (1, 3, 4, 5, 6A, 6B, 7F, 9V, 14, 18C, 19A, 19F, 23F) antibody concentrations, depending on the GSK laboratory or WHO reference laboratory assay cut-offs, will be calculated along with its exact 95% CI [Clopper, 1934].
- Percentage of subjects with anti-D and anti-T antibody concentrations ≥ 1.0 IU/ml will be calculated along with its exact 95% CI [Clopper, 1934].
- Percentage of subjects with anti-PRP antibody concentrations ≥ 1.0 $\mu\text{g/ml}$ and anti-HBs antibody concentrations ≥ 100 mIU/mL will be calculated along with its exact 95% CI [Clopper, 1934].
- GMC/GMT with 95% CI will be tabulated for antibodies against each antigen.
- The booster response rates to PT, FHA and PRN (with exact 95% CI) one month after the booster dose will be calculated.

The above summaries will be provided by country or primary vaccination schedule for countries involving more than 50 subjects.

- The distribution of antibody concentrations/titres for each antigen will be displayed using reverse cumulative distribution curves (RCCs).
- The distribution of antibody concentrations or titres of each antigen will be tabulated.

Handling of missing data:

- For a given subject and a given immunogenicity measurement, missing or non-evaluable measurements will not be replaced. Therefore, an analysis will exclude subjects with missing or non-evaluable measurements.

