5.3.2. Additional considerations

Considering that RCC are available and the percentage of subjects with titres/concentration above key thresholds are available, the distribution of antibody concentrations or titres of each antigen will not be tabulated.

Following the re-validation of the pertussis assays, the booster response to the PT, FHA and PRN antigens is defined as:

- for subjects with pre-vaccination antibody concentration below the assay cut-off, post-vaccination antibody concentration \geq four times the assay cut-off,
- for subjects with pre-vaccination antibody concentration between the assay cut-off and below four times the assay cut-off, post-vaccination antibody concentration \geq four times the pre-vaccination antibody concentration, and
- for subjects with pre-vaccination antibody concentration \geq four times the assay cut-off, post-vaccination antibody concentration \geq two times the pre-vaccination antibody concentration

Percentage of subjects with anti-pneumococcal serotypes (1, 3, 4, 5, 6A, 6B, 7F, 9V, 14, 18C, 19A, 19F, 23F) above the assay cut-offs, will be calculated along with its exact 95% CI [[Clopper](#), 1934].

In addition to the percentage of seroprotected or seropositive subjects, the percentage of subjects above the assay cut off and percentage of subjects above the following cut-off will be summarized

- Anti-PRP antibody concentrations \geq 1.0 $\mu\text{g/mL}$.
- Anti-diphtheria antibody concentrations \geq 1.0 IU/mL.
- Anti-tetanus antibody concentrations \geq 1.0 IU/mL.
- Anti-HBs antibody concentrations \geq 100 mIU/mL.
- Anti-pneumococcal serotypes (1, 3, 4, 5, 6A, 6B, 7F, 9V, 14, 18C, 19A, 19F, 23F) \geq 0.35 $\mu\text{g/mL}$.

In addition, subgroups analysis according to gestational age (27-32 weeks and 33-36 weeks) and age of the mother at dose 1 in the primary study (18-24 year, 25-34 year and 35-45 year) will be performed.

The sub-group analyses will be limited to descriptive tables of GMT/GMC and the percentage of subjects with titres/concentration above key thresholds for ATP cohort of immunogenicity.

In light of the number of subjects enrolled in each country, the analysis by country will be replaced with analysis by schedule of the primary vaccination (2 doses ie 2,4 months combined with 3,5 months versus 3 doses i.e. 2,3,4 months combined with 2,4,6 months).

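### SAP elimination code 2120 lets an undefined abnormal serology pattern remove infants from the primary cohort, and that ground overlaps the pertussis booster-response endpoint

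*SAP*

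**What the plan says.** SAP 5.3.1 states: "The primary analysis will be based on the ATP cohort for analysis of immunogenicity". SAP 4.2.3.1 then lists the codes that remove a subject from that cohort. Code 2120, applied at Visit 3, names three grounds, "Obvious incoherence, abnormal serology evolution or error in data", and adds two examples in brackets: a mismatch between CRF and results, and mislabelled samples.

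The primary endpoint in SAP 3.3 includes "Booster response to PT, FHA and PRN antigens, one month after the booster dose". SAP 5.3.2 defines that response by three rules, chosen by the pre-booster level:

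- below the assay cut-off: post-booster at least four times the cut-off;
- from the cut-off to below four times the cut-off: post-booster at least four times the pre-booster value;
- at or above four times the cut-off: post-booster at least twice the pre-booster value.

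The ATP criteria in protocol 10.4.4 and SAP 4.1.4 cover eligibility, doses, intervals, forbidden products, medical conditions and availability of results. On the last of these the SAP says: "This will include subjects for whom assay results are available for antibodies against at least one study vaccine antigen component after vaccination". Neither list has a criterion based on how the antibody values change. SAP section 8, on changes from planned analyses, does not name one either.

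Three provisions bear on the consequences. SAP 4.2.1 removes infants from the TVC only for codes 1030 and 900. SAP 5.3.1 adds a TVC immunogenicity analysis if more than 5% of enrolled subjects in any group are excluded from the ATP cohort. SAP 5.1.2 tabulates eliminations by reason and group.

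**The concern.** The pertussis part of the primary endpoint is itself a judgement on the change from the pre-booster to the post-booster sample. An exclusion that looks at the same change can depend on the outcome. The three grounds in code 2120 are alternatives. The bracket illustrates incoherence and data error, and neither example says what makes a serology course abnormal. Untestable or missing post-booster results already have their own code, 2100, so what the phrase adds to the list is mainly exclusion on the value itself.

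At stake is the estimate in each group and the descriptive comparison between groups. The protocol background reports slightly weaker primary responses in infants of vaccinated mothers, said not to persist after the booster. If weak booster responders were more frequent in one group and some were coded 2120, that group's rate would rise and a visible difference would shrink. No hypothesis test is affected, because all analyses are descriptive.

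**Working it through.** **Inputs.** Maximum enrolment is about 340 per group (protocol 5.2.2.1.1). Evaluable numbers in protocol 10.3 follow from a 20%, 30% or 40% reduction: 340 × 0.80 = 272, 340 × 0.70 = 238, 340 × 0.60 = 204. Reference booster-response rates in protocol Table 17 go as low as 86.0% (FHA) and 93.3% (PT), both from study 095. The number of infants coded 2120 is not given anywhere in the plan. I assume a range of 1 to 5 non-responders dropped per group.

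**Reproducing the plan's figures.** With the exact two-sided 95% Clopper-Pearson interval, 234/272 = 86.0% (81.3–89.9), 190/204 = 93.1% (88.8–96.2) and 226/238 = 95.0% (91.4–97.4), as in Table 16. All 33 rows of that table reproduce to within 0.1 point when the responder count is the whole number just below or just above N × rate.

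**Effect of dropping non-responders.** With x responders among N, removing k non-responders changes the rate from x/N to x/(N − k). For k = 1 the increase is x/N ÷ (N − 1). At 234/272 this is 0.860/271 = 0.32 points; at 200/204 it is 0.980/203 = 0.48 points. Rates in percent:

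| x/N | none dropped | 1 dropped | 3 dropped | 5 dropped |
|---|---|---|---|---|
| 234/272 | 86.0 (81.3–89.9) | 86.3 | 87.0 | 87.6 (83.1–91.3) |
| 222/238 | 93.3 (89.3–96.1) | 93.7 | 94.5 | 95.3 (91.7–97.6) |
| 190/204 | 93.1 (88.8–96.2) | 93.6 | 94.5 | 95.5 (91.6–97.9) |

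Five dropped infants therefore add 1.6 points (first row) to 2.3 points (last row). The 95% interval at 190/204 is 96.2 − 88.8 = 7.4 points wide.

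**Which infants overlap with the code.** An infant who starts at or above four times the cut-off and rises 1.9-fold is a non-responder with an ordinary rise. So is one who starts between the cut-off and four times the cut-off and rises 3-fold. Only flat or falling courses are both booster failures and plausibly abnormal. The code also removes the whole infant: an infant flagged for one antigen who responded to another leaves that other rate slightly lower, for example by 38/(272 × 271) = 0.05 points at 234/272.

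**Seroprotection.** This depends on the post-booster value alone, so an infant whose titre falls but stays above the threshold counts as protected, and removing that infant does not raise the rate. Reference seroprotection in Table 17 is 98.5% to 100%, except 91.6% for HBs in pre-term infants. At 98.5% of 204 infants there are about 204 × 0.015 = 3 who are not protected, so little can be inflated.

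**The 5% trigger.** 5% of 340 is 17. In the extreme case that 17 infants, all non-responders, are the only exclusions in the group, the trigger does not fire, and the rate moves from 292/340 = 85.9% to 292/323 = 90.4%, or from 317/340 = 93.2% to 317/323 = 98.1%. This is a ceiling and not an expectation. If the 20–40% reduction counts as exclusion of enrolled infants, it is 68 to 136 of 340, well over 17, and the TVC analysis runs.

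**The case against.** The strongest reply is that the code is about data integrity. It opens with a word limiting it to obvious cases and closes with a mismatch between CRF and results and with mislabelled samples. An implausible course is often how a sample swap is first noticed, and a swap spoils two infants' data. Nothing in either document says that non-responders are to be eliminated. An isolated weak pertussis result would be poor evidence of a swap if the other antigens rose, and an implausibly high result could be coded too. SAP 4.2 can be read as operational detail for the cohort definitions, and protocol 10.5 already leaves out non-evaluable measurements. Coded infants stay in the TVC, whose analysis is likely to be triggered, and eliminations are tabulated by reason.

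Much of this stands. The intent is probably data error, only flat or falling results overlap with the endpoint, and the count is probably small. The mock table for exclusions shows a single such case among 1200, but it was copied from another study and says nothing about frequency here.

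It does not close the point. The phrase remains a separate ground without a rule. The protocol's provision on non-evaluable data concerns single measurements, whereas code 2120 removes a subject. The TVC analysis is conditional and restores nearly all exclusions at once, so it cannot show what code 2120 did. The tabulated row combines the three grounds and shows no antibody values.

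A reader might also infer that the person assigning the code will know the group, since the protocol says "the data related to the study groups will be unblinded at the end of study 116945". The documents do not support that. Protocol 5.3 keeps the laboratory blinded and site staff blinded until that study is unblinded, and no text says who assigns the code. What can be said is that blinded assignment is not required.

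**Conclusion.** The point holds as a gap in the exclusion rule: an undefined ground, absent from the ATP definitions, acts on the primary cohort and overlaps the pertussis booster response for infants with flat or falling concentrations. The size is about 0.3 to 0.5 percentage points per dropped non-responder at 204 to 272 evaluable infants per group, and 1.6 to 2.3 points in the tabulated examples if five are dropped. The number dropped is an assumption; the plan gives none, and it is probably small.

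A reader might go further and infer that the plan will remove booster non-responders as a class, or that seroprotection rates will be materially inflated. The documents support neither. The bracketed examples point to data error, many non-responders would have an unremarkable rise, and seroprotection does not depend on the change from the pre-booster value. Because the study is descriptive and the coded infants remain in the TVC, this is a cheap improvement and not a flaw that undermines the primary analysis.

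**What to change.** - In SAP 4.2.3.1, let an abnormal serology pattern prompt a query to the site and laboratory. Exclude under code 2120 only when a sample or data error is confirmed independently of the antibody value.
- State that the decision is made without knowledge of group.
- List every infant given code 2120 with pre- and post-booster values and the confirmed error.
- Report the primary pertussis booster-response rates, and the seroprotection rates, once with these infants kept, whether or not the 5% trigger is met.

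The cost is one wording change, one listing and one sensitivity row per endpoint. The downside is that an occasional unconfirmed sample swap stays in the cohort and slightly lowers the rate.

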5. STATISTICAL ANALYSES

Note that standard data derivation rules and stat methods are described in “business rules document” and will not be repeated below. The study specific data derivation rules and stat methods will be described in section 9.

5.1. Demography

5.1.1. Analysis of demographics/baseline characteristics planned in the protocol

Demographic characteristics (age in months, race, length [cm], weight [kg], head circumference [cm]), cohort description and withdrawal status will be summarised by group using descriptive statistics:

- Frequency tables will be generated for categorical variables such as race, country or primary vaccination schedule (2 dose vs. 3 dose in study 048);
- Mean, median and standard error will be provided for continuous data such as age.

The distribution of subjects enrolled among the study sites will be tabulated as a whole and per group.

5.1.2. Additional considerations

Gender, country, maternal age group (18-24Y, 25-34Y and 35-45Y) and gestational age at dose 1 in the primary study (27-32W, 33-36W) will also be summarised by group using above mentioned descriptive statistics.

All demography summaries will be generated for the TVC. The summary of age, length[cm], Weight [kg], head circumference, gender will also be provided for the ATP cohort for immunogenicity.

Number and reason for elimination from ATP cohorts will be tabulated by group.

Quartile 1 and quartile 3 will be provided for continuous data such as age in months, race, length [cm], weight [kg], head circumference [cm], body mass index in [kg/m²].

5.2. Exposure

NA.

5.2.1. Analysis of exposure planned in the protocol

NA.

5.2.2. Additional considerations

The doses administered will be summarized by vaccine.

5.3. Immunogenicity

5.3.1. Analysis of immunogenicity planned in the protocol

The primary analysis will be based on the ATP cohort for analysis of immunogenicity. If in any vaccine group, the percentage of enrolled subjects excluded from this ATP cohort is more than 5%, a second analysis based on the TVC will be performed to complement the ATP analysis. All analyses will be descriptive.

For each group, at each time point that a blood sample result is available:

- Seropositivity rates against PT, FHA and PRN antigens and pneumococcal antigens (1, 3, 4, 5, 6A, 6B, 7F, 9V, 14, 18C, 19A, 19F, 23F) with exact 95% CI [Clopper, 1934] will be calculated.
- Seroprotection rates against diphtheria toxoid, tetanus toxoid, HBs, PRP antigen and poliovirus types 1, 2, 3 antigens (with exact 95% CI [Clopper, 1934]) will be calculated.
- Percentage of subjects with anti-pneumococcal serotypes (1, 3, 4, 5, 6A, 6B, 7F, 9V, 14, 18C, 19A, 19F, 23F) antibody concentrations, depending on the GSK laboratory or WHO reference laboratory assay cut-offs, will be calculated along with its exact 95% CI [Clopper, 1934].
- Percentage of subjects with anti-D and anti-T antibody concentrations ≥ 1.0 IU/ml will be calculated along with its exact 95% CI [Clopper, 1934].
- Percentage of subjects with anti-PRP antibody concentrations ≥ 1.0 $\mu\text{g/ml}$ and anti-HBs antibody concentrations ≥ 100 mIU/mL will be calculated along with its exact 95% CI [Clopper, 1934].
- GMC/GMT with 95% CI will be tabulated for antibodies against each antigen.
- The booster response rates to PT, FHA and PRN (with exact 95% CI) one month after the booster dose will be calculated.

The above summaries will be provided by country or primary vaccination schedule for countries involving more than 50 subjects.

- The distribution of antibody concentrations/titres for each antigen will be displayed using reverse cumulative distribution curves (RCCs).
- The distribution of antibody concentrations or titres of each antigen will be tabulated.

Handling of missing data:

- For a given subject and a given immunogenicity measurement, missing or non-evaluable measurements will not be replaced. Therefore, an analysis will exclude subjects with missing or non-evaluable measurements.

